| 15-16 | Modification of treatment materials based on developmental pilot study |
| 17-18 | Review and feedback from study team and consultants; finalize intervention and materials |

 Table 1. Expected Timeline of Intervention Development (Study 1)

Feasibility Assessment. Despite a lack of standard methods for assessing feasibility, recent reviews have described several areas in which feasibility can be examined to support larger or more comprehensive studies (e.g., Arain et al., 2010; Bowen et al., 2009). The current pilot

study will examine three feasibility constructs that seem particularly relevant, as a prelude to the subsequent RCT:

1) Acceptability of the intervention will be assessed during as well as at the end of the treatment phase and at follow-up assessments, as follows: (1) Client Satisfaction Questionnaire (CSQ; Attkisson & Greenfield, 1994), a standard assessment of treatment satisfication; (2) a questionnaire developed for this study that asks the participant to evaluate specific aspects of the intervention workbook and counseling sessions; and (3) in-depth interviews conducted by the PI, a Co-I, or a member of the research staff using a series of guided questions to further glean reactions to specific treatment components, to follow-up on questionnaire answers, and to gather more nuanced information that could guide revisions to the intervention. In addition, we will attempt a structured telephone interview with any participant who drops out of the study early, in order to ascertain reactions to treatment and potential reasons for early withdrawal. Finally, study counselors will complete an evaluation form following each session. Other indices of acceptability will be the rate of adherence to both behavioral (i.e., completing assignments in the FE workbook) and pharmacological (i.e., smoking VLNC cigarettes as prescribed) instructions.

2) Demand will be estimated by noting accrual rates into the study. To quantify accrual, we will calculate recruitment costs per participant, with a target benchmark of \leq \$100 based on our previous clinical trials.

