Based on participant and counselor feedback from Study 1, the FE workbook was converted to a series of weekly booklets. The content is similar to what was included in the pilot study, but the workbook series now includes additional cessation-related advice and enhanced graphics. The targeted intervention will consist of the FE workbook series and supportive counseling (as developed and refined in Study 1), whereas the standard intervention will consist of the "Clearing the Air" booklet (National Cancer Institute; NIH Publication No. 11-1647), along

with a brief study introduction booklet which will explain the rationale for using reduced nicotine cigarettes as a cessation aid. Additionally, the standard intervention will entail an equal duration (relative to targeted intervention) of cognitive-behavioral smoking cessation counseling that follow recommendations from the USPHS Clinical Practice Guidelines along with supplemental handouts (Fiore et al., 2008). Counseling sessions for all conditions will include discussion of compliance with smoking only study cigarettes, as well as other study procedures. Although all participants will be strongly encouraged to smoke only study cigarettes, they will be told there is not a penalty for use of non-study cigarettes, and that it is crucial for them to report any use of non-study cigarettes or other nicotine or tobacco products. The VLNC immediate and gradual tapering conditions will be as described above, with participants, counselors and experimenters blind as to condition assignment.

Target Quit Date Participants will attend a session on their Target Quit Date. During this visit, all study cigarettes distributed during their prior visit will be collected, additional cessation counseling will be provided, physiological measures (i.e., carbon monoxide, breath alcohol, blood pressure, and heart rate) will be collected, and possible health changes will be assessed. Participants will also complete a Cigarette Evaluation Scale for their study cigarettes, the QSU for their study and usual brand cigarettes, the Drug Effects/Liking Scale for their study cigarettes to obtain intermediate smoking-related outcomes: cue-reactivity and cigarette purchase task (see descriptions below). Lastly, those randomized to the targeted intervention will be provided with the final Countdown booklet.

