detailed screening/baseline session at the Tobacco Research and Intervention Program (TRIP) of the Moffitt Cancer Center. During this session, informed consent will be obtained, followed by administration of questionnaire and interview-based assessments to determine eligibility based on inclusion/exclusion criteria (see below). Eligible participants will receive study cigarettes for five weeks, using either an immediate or gradual tapering regimen. All participants will receive written materials to assist in their quit attempt, as well as in-person smoking cessation counseling. In the RCT only, participants will engage in two intermediate tests of smoking behavior, and will attend follow-up sessions 2- and 6-months following a target quit date (TQD). Participants will be compensated for attendance at treatment and follow-up sessions, for completing workbook assignments and data collection activities, and for their performance on smoking behavior tests. The potential compensation for each participant in the developmental pilot study (Study 1) is \$200, and for the RCT (Study 2) the potential compensation is \$260. The eligibility criteria for both studies are as follows:

Inclusion criteria: (a) \geq 18 years of age; (b) smoke at least 5 cigarettes daily for the past year; (c) expired-air carbon monoxide (CO) > 8 ppm (if \leq 8 ppm, then NicAlert Strip > 2); (d) current motivation to quit smoking; and (e) able to speak and read English sufficiently for completion of consent form and questionnaires.

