Collection and Reporting of AEs and SAEs. At each study visit, participants will be asked to report any negative health changes on the 'Health Changes Questionnaire' since the prior visit. Any negative changes will be recorded on an Adverse Event (AE) form. This form will include fields for describing the adverse event, as well as the onset, duration, status (completed vs. ongoing), and any steps taken to resolve the AE. The form will be reviewed by the study physician (or by the study investigators during the follow-up phase) prior to the next study visit, and the AE will be monitored until it is marked as resolved. All AEs will be assessed to determine if they meet criteria for an SAE. Monitoring by the PI will be conducted on an ongoing basis and monitoring by the IRB is conducted at the continuing reviews as scheduled by the IRB and upon receiving reports of AEs from the PI.

Management of SAEs and Other Study Risks. Serious adverse events (SAEs), as defined by the FDA, will be systematically evaluated at each study visit. All product-related adverse events of a non-serious nature will be reported to the IRB at the time of annual renewal. Any SAE, whether or not related to study product or participation, will be reported to the IRB, the study sponsor (State of Florida Department of Health), and the FDA. A participant may be discontinued from the study or withheld from study product if the study physician (or his designee) determines it is the best course of action in order to protect the safety of the participant. In the event that a participant either withdraws from the study or the investigator or study physician(or licensed medical professional designated to consult in his absence) decides to discontinue a participant due to an SAE, the participant will have appropriate follow-up medical monitoring. The participant experiencing a SAE will be followed until the problem resolved, stabilizes, or is clearly unrelated to the study cigarettes. Outcome of SAEs will be periodically reported and a summary of SAEs will be provided in study progress reports to the IRB, sponsor, and FDA.

Stopping Rules. For the participant's protection, participants will be withdrawn immediately from the study if any of the following occur:

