- Cardiovascular disease (CVD) event: typically includes MI (heart attack), PTCA (angioplasty/stenting), bypass surgery, stroke, peripheral vascular disease (arterial blockages in arms or legs leading to procedure or surgery). Less common CVD problems would be new cardiac arrhythmias (e.g., new atrial fibrillation) or new valvular disease (e.g., mitral or aortic regurgitation.)
- 2. DVT/PE (deep vein thrombosis/pulmonary embolism, i.e., blood clots in the venous system)
- 3. Suicide Attempt: A participant will be withdrawn if he/she attempts suicide at any time during participation in the study.
- 4. Psychiatric Hospitalization: A participant will be withdrawn if he/she is hospitalized for psychiatric reasons at any time during participation in the study.
- 5. Pregnancy: If a participant indicates she is pregnant or has a positive pregnancy test, she will be withdrawn from the study. Approximately 30 days after being withdrawn, the research staff will contact the participant to confirm her due date. This event will remain open until delivery. At that time the study physician (or licensed medical professional designated to consult in his absence) will contact the participant to ask a few questions about the baby's health and will update the open 'Adverse Event Form'.
- 6. Expired breath CO increase: A participant will be withdrawn from the study if the average of two consecutive CO readings during the same visit is 100 ppm or greater.

Withdrawal Rules: In order to detect significant increases in smoking due to study cigarettes (e.g., compensatory smoking), which could signal increased cardiovascular risk, we will apply guidelines for discontinuation of VLNC smoking due to marked increases in carbon monoxide (CO) levels or smoking, as follows:

- a) If the average of two consecutive CO readings during the same visit is 100 ppm or greater
- b) If both of the following criteria are met for two consecutive weeks:
 - 1. Cigarettes per day (CPD) increase: The average CPD increases by more than 100% from the average CPD during baseline
 - 2. Expired breath CO increase; If the average of two consecutive CO measurements in the same visit is:
 - i. CO is greater than 50 ppm if CO at baseline is < 20 ppm
 - ii. CO is greater than 60 ppm if CO at baseline is 20 34 ppm
 - iii. CO is greater than 70 ppm if CO at baseline is 35 49 ppm
 - iv. CO is greater than 80 ppm if CO at baseline is 50 64 ppm
 - v. CO is greater than 90 ppm if CO at baseline is 65 80 ppm

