The CO stopping criteria are derived from recent and ongoing large scale (multi-site) trials with reduced nicotine cigarettes (U54 DA031659; MPI's: [name], [name]). The criteria represent CO increases of two types: (1) absolute, based on an unacceptable CO level (i.e., 100 ppm) at any study visit, and (2) relative, adjusted according to individually determined baseline values. As CO can be quite variable, relative values are intended to balance increases in individual risk while accounting for baseline values.

The following will be monitored and can lead to the participant being withdrawn by the PI or study physician (or licensed medical professional designated to consult in his absence):

- 1. Cigarettes per day increase: Continued participation will be evaluated by the site PI if the average number of cigarettes per day (CPD) increases by more than 100% from the average CPD at baseline.
- Blood pressure (BP) or heart rate (HR) changes: If any of the following occur postenrollment: 1) BP is at or above 160/100 or below 90/50, or 2) HR is at or above 105 bpm or below 45 bpm a manual blood pressure and heart rate measurement will be taken after 10 minutes have passed.
- 3. Expired breath CO increase: If the average of two consecutive CO measurements in the same visit is:
 - i. CO is greater than 50 ppm if CO at Baseline is <20 ppm.
 - ii. CO is greater than 60 ppm if CO at Baseline is 20 34 ppm.
 - iii. CO is greater than 70 ppm if CO at Baseline is 35 49 ppm.
 - iv. CO is greater than 80 ppm if CO at Baseline is 50 64 ppm.
 - v. CO is greater than 90 ppm if CO at Baseline is 65 80 ppm.
- 4. Any hospitalization or debilitation in which participation in the study could be detrimental to the recovery process. This will be self-reported by the participant and will be reviewed by the PI and study physician (or licensed medical professional designated to consult in his absence) to determine whether continued participation in the study is appropriate.
- 5. If a participant is behaving in an inappropriate or threatening manner, admits to lying about eligibility criteria, is participating in other smoking research studies that could affect the primary outcome measures, or is not complying with key study procedures.

Potential Benefits of the Proposed Research to the Subjects and Others

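### The six Stopping Rules end study participation rather than study cigarettes, and no text keeps the 2- and 6-month abstinence outcomes of those withdrawn: a minor gap, cheap to close

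*Combined protocol and SAP*

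**What the plan says.** **The rule.** Stopping Rules (Section E) states that "participants will be withdrawn immediately from the study if any of the following occur". The six triggers are a cardiovascular event, DVT/PE, a suicide attempt, psychiatric hospitalisation, pregnancy, and CO averaging 100 ppm or more. None is limited to the weeks on study cigarettes. The psychiatric rule applies to anyone "hospitalized for psychiatric reasons at any time during participation in the study", and the suicide-attempt rule has the same open window.

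**Product-only wording elsewhere.** Management of SAEs and Other Study Risks lets the study physician either discontinue a participant or withhold product, so the authors distinguish the two. The six rules do not offer the second choice. For CO the text gives both consequences. Item 6 says "A participant will be withdrawn from the study if the average of two consecutive CO readings" reaches 100 ppm, while Withdrawal Rules lists the same threshold among "guidelines for discontinuation of VLNC smoking due to marked increases in carbon monoxide".

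**Product window.** Human Subjects Involvement says "Eligible participants will receive study cigarettes for five weeks". At the Target Quit Date (TQD) visit "all study cigarettes distributed during their prior visit will be collected".

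**Contacts after withdrawal.** Those described are medical monitoring after an SAE, calls about due date and the baby's health, a paid visit to return product, and, in the Study 1 feasibility text, a "structured telephone interview with any participant who drops out of the study early" about reactions to treatment and reasons for leaving. None is said to collect smoking status. Follow-up Assessments offers telephone and then mail to people who cannot or will not attend, and does not say whether withdrawn participants are included.

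**Outcome and analysis.** Aim 2 makes 7-day point prevalence abstinence at each follow-up the primary outcome and cites tolerance of data missing at random. Sample Size Determination names an intent-to-treat approach.

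**The concern.** A safety rule should stop the exposure that may cause harm. It need not stop the collection of an outcome that takes one telephone call. Here the stated consequence of a post-randomisation event is removal from the study, while the power statement rests on intent-to-treat. If staff follow the rule literally, someone withdrawn in the product phase contributes neither primary observation, and someone withdrawn at the 2-month visit loses the 6-month one.

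Of the six triggers, high CO is the one plainly tied to smoking, so those losses fit poorly with a missing-at-random rationale. After the TQD there is also nothing left to stop. CO is read at both follow-ups, and the text explaining the CO criteria applies the 100 ppm limit at any visit. A relapsed participant reading 100 ppm at 2 months would leave the study with no study product to withhold.

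**Working it through.** **1. Where outcomes can be lost**

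The Appendix schedule puts only the 2- and 6-month visits after the TQD, and health changes are asked about at visits.

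| When the event occurs | When it normally surfaces | Primary observations at risk |
|---|---|---|
| Product phase (five weeks) | Weekly visit or TQD | 2- and 6-month |
| TQD to 2 months | 2-month visit, where smoking status is also taken | 6-month |
| 2 to 6 months | 6-month visit, where smoking status is also taken | Usually none |

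A participant who reports an event between visits could be withdrawn sooner.

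**2. The plan's power figure**

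Inputs from Sample Size Determination: 104 per intervention level, 20% abstinence with the standard intervention, about 18 points' improvement, two-sided alpha 0.05, power 0.80.

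Formula (pooled variance under the null): power = Φ[(d − 1.96·s0)/s1], where d = p2 − p1, s0 = √[p̄(1−p̄)(1/n1 + 1/n2)], p̄ is the pooled rate, and s1 = √[p1(1−p1)/n1 + p2(1−p2)/n2].

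- 20% vs 38%, 104/104: p̄ = 0.29, s0 = 0.0629, s1 = 0.0617, power = **0.821**.
- The difference giving 0.80 power is 17.5 points (0.801), which agrees with the plan's approximate 18.

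**3. Expected attendance**

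The note to Table 2 expects 148 sessions at 2 months and 138 at 6 months. At 6 months 208 − 138 = 70 are absent (34%). With equal attrition, 138/2 = 69 per level: s0 = 0.0773, s1 = 0.0757, power = **0.647**.

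**4. Illustrative withdrawals**

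The documents give no event rate, so I assume k = 2 or k = 5 people, all at one level. Two readings are possible and should not be mixed. Ranges show which level is affected.

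| Reading | k = 2 | k = 5 |
|---|---|---|
| Lost in addition to the 70 (69 − k vs 69) | 0.640–0.641 | 0.628–0.632 |
| Already among the 70, and retained by the fix (69 + k vs 69) | 0.653–0.654 | 0.661–0.664 |

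Either way the change from 0.647 is about 0.01 for k = 2 and 0.01 to 0.02 for k = 5.

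**5. Shift in the estimated rate, first reading only**

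Omitting k people whose true abstinence is q from a level with true rate p shifts that level by (69p − kq)/(69 − k) − p. With p = 0.20 or 0.38 and q from 0 to 0.38:

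- k = 2: −0.5 points (p = 0.20, q = 0.38) to +1.1 points (p = 0.38, q = 0).
- k = 5: −1.4 to +3.0 points at the same two extremes.

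The sign depends on q, which is unknown, and the target difference is 18 points.

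**The case against.** The best reply is that no sentence ends outcome collection on withdrawal. The plan names intent-to-treat, the telephone and mail routes do not exclude withdrawn participants, and the double treatment of CO suggests that withdrawal may be meant loosely. This stands in part: the loss is the natural reading of being withdrawn from the study, not an explicit statement. A reader might infer that the protocol forbids further outcome contact, and the documents do not say so.

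A reader might also infer that open-ended timing costs outcomes throughout follow-up. The visit schedule does not support that. After the TQD most events surface at a visit where smoking status is measured anyway, so the exposure lies mainly before or at the 2-month visit.

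A third tempting step is to add withdrawal of someone who "is not complying with key study procedures" to the smoking-related losses. That item is in the separate discretionary list, where events can lead to withdrawal but need not, and it is not one of the six rules.

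Two limits on the arithmetic also stand. The one-sided counts are assumed, and most triggers have no evident link to arm. The 148 and 138 are session counts in a workload note, and remote follow-up could add outcomes beyond them. Finally, the two events with the explicit open window, suicide attempt and psychiatric hospitalisation, are those where a physician may well advise against contact, so the fix may change little for them.

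**Conclusion.** The point holds as a minor, cheap improvement. Followed as written, the six rules take people out of the study for post-randomisation events, and nothing preserves their remaining primary outcomes. CO of 100 ppm or more needs a single instruction.

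The size is not derivable from the documents and is probably small: one or two hundredths of power under assumed one-sided counts of 2 or 5, with equal background attrition. The documents do not support a claim of material bias. The direction is unknown, and the effect is minor beside the 34% absence already expected at 6 months. The case for change is that the loss is avoidable at almost no cost.

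**What to change.** - Keep all six safety triggers. Make the consequence stopping study cigarettes and, where clinically needed, study procedures.
- Give CO of 100 ppm or more one consequence, and say what it means after the TQD when no study cigarettes remain.
- State that the 2- and 6-month smoking-status contacts continue by the telephone or mail routes in Follow-up Assessments, unless the participant withdraws consent or the study physician judges contact harmful.
- State that these participants are analysed as randomised.

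The cost is protocol wording and at most two brief contacts per affected participant through channels that already exist. Safety triggers and sample size do not change.

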Appendix

FSC-RNC STUDY 2 TABLE: PROCEDURES BY VISIT

| Assessment Name | Platform | Visit 1 Screen | Visit 2 | Visit 3 | Visit 4 | Visit 5 | Visit 6 | 2Month Follow- Up | 6Month Follow-Up | |
|--|-----------------------|--|------------|------------|------------|------------|------------|-------------------------|---------------------|--|
| Telephone Recruitment Questionnaire | REDCap | N/A, administered via the telephone prior to the first visit | | | | | | | | |
| VISITASSESSMENTS | | | | | | | | | | |
| Weight (Height at screen only) | Paper and REDCap | х | х | х | х | х | х | х | х | |
| Pregnancy Test (if applicable) | Paper and REDCap | х | | х | | | х | | | |
| Heart Rate & BP | Paper and REDCap | х | х | х | х | х | х | х | х | |
| CO Reading | Paper and REDCap | х | х | х | х | х | х | х | х | |
| NicAlert (if CO ≤8 ppm) | Paper and REDCap | х | | | | | | | | |
| Breath Alcohol Test | Paper and REDCap | х | х | х | х | х | х | х | х | |
| Urine Toxicology | Paper and REDCap | х | | | | | | | | |
| Concomitant Medications | Paper and REDCap * | х | х | х | х | х | х | х | х | |
| Health Changes Questionnaire | Paper and REDCap * | | х | х | х | х | х | х | х | |
| Adverse Events | Paper and REDCap * | | Х | х | х | х | х | х | х | |
| Product Accountability Log | Paper and REDCap | х | Х | х | х | х | х | | | |
| Counseling Session Notes | Paper (Source only) * | х | х | х | х | х | х | | | |
| Study Expectations Agreement Form | Paper (Source only) * | х | | | | | | | | |
| Address Change Sheet | Paper (Source only) * | | х | | | | х | | | |
| Contact Sheet | Paper (Source only) * | | х | | | | Х | | | |
| Tobacco Use History and Exposure | Paper and REDCap ** | х | | | | | | | | |
| Smoking Cessation Therapy | Paper and REDCap ** | х | | | | | | | | |
| FTND | Paper and REDCap ** | х | | | | | | | | |
| DemographicInformation | Paper and REDCap ** | х | | | | | | | | |
| Brief Medical History | Paper and REDCap ** | х | | | | | | | | |
| Prime MD | Paper and REDCap ** | х | | | | | | | | |
| Contemplation Ladder | Paper and REDCap ** | х | | | | | | | | |
| Brief NCQ | Paper and REDCap ** | х | | | | | | | | |
| BSCQ-A | Paper and REDCap ** | х | | | | | | | | |
| Brief WISDM | Paper and REDCap ** | х | | | | | | | | |
| MINI Intl. Neuropsychiatric Interview (M.I.N.I.) | Paper (Source only)** | х | | | | | | | | |

